12.5 CCI

CCI

[Redacted content]

- CCI [Redacted]

CCI [Redacted]

[Redacted]

[Redacted]

[Redacted]

[figure not shown]
[Redacted]

[Redacted]

[Redacted]

[Redacted]

CCI

13 Safety

13.1 Adverse Events

13.1.1 General Methodology for Adverse Events

Unless otherwise specified, tables, graphs, and listings will be based on the APTS.

All the tables and graphs will be presented by treatment group.

Tables by preferred term and tables by system organ class (SOC) and preferred term will be sorted in descending order based on the percentages of participants with these adverse events in the_Lu AG09222 CCI group.

Unless otherwise specified, the summaries of adverse events will include the number and percentage of participants with an adverse event and number of events. In tables displaying SOC or preferred terms, participants are counted only once within each SOC or preferred term.

Listings of adverse events will be sorted by site, treatment group, participant screening number, preferred term, verbatim, adverse event start date, adverse event stop date, the date of IMP infusion, the time since IMP infusion, duration of the adverse event, date of death, action taken, causality, intensity, seriousness, and outcome.

For adverse events that change in intensity, each intensity will be included. In listings of adverse events, start or stop dates will be displayed as collected also in case of partially or completely missing dates.

13.1.2 Coding of Adverse Events

Adverse events will be coded using MedDRA, Version 25.0 or later.

13.1.3 Classification of Adverse Events

Adverse events will be classified according to the time of onset of the adverse event:

- *pre-treatment adverse event* – an adverse event that starts on or after the date the participant signed the *Informed Consent Form* and prior to the date and time of the dose of IMP.
- *treatment-emergent adverse event (TEAE)* – an adverse event that starts during or after administration of the dose of IMP, or a pre-treatment adverse event that increases in intensity or becomes serious during or after administration of the dose of IMP.

For handling of adverse events with incomplete start dates to facilitate this classification, see section 22.3.5. Note that adverse events with incomplete start dates will be classified as treatment-emergent simply if the imputed start date is on or after the date of IMP infusion, since the start time of the adverse event will not be imputed, unless the investigator in such a case has assessed that the causality to IMP is *not related - prior to IMP*.

An adverse event is considered causally related to the use of the IMP when the causality assessment by the investigator is *probable* or *possible*. If the causality assessment is missing, the adverse event is considered possibly causally related.

13.1.4 Presentation of Adverse Events

All adverse events will be listed for the APRS, including a flag for TEAEs.

An overview of the numbers and percentages of participants with TEAEs, serious adverse events (SAEs), TEAEs leading to infusion interruption, TEAEs leading to withdrawal, and of participants who died will be provided based on the APTS. For TEAEs, SAEs, and TEAEs leading to withdrawal, the total number of events will be included.

All pre-treatment adverse events will be summarized and listed for the APRS, separately.

13.1.5 Presentation of Treatment-emergent Adverse Events

The following summaries will be provided for the APTS:

- TEAEs by SOC and preferred term
- TEAEs by preferred term
- TEAEs by sex and preferred term
- TEAEs with an incidence $\geq 2\%$ and 5% in any treatment group by preferred term
- causally related TEAEs by SOC and preferred term
- TEAEs by severity (*mild/moderate/severe*), SOC, and preferred term
- causally related TEAEs by severity, SOC, and preferred term
- TEAEs occurring on the day of dosing after infusion start by SOC and preferred term

For TEAEs occurring on the day of dosing after infusion start, TEAEs with missing start times will also be included.

13.1.6 Presentation of Deaths

All the adverse events in participants who died will be listed for the APRS.

13.1.7 Presentation of Serious Adverse Events

All the SAEs will be listed for the APRS.

Treatment-emergent SAEs for the APTS will be summarized by:

- SOC and preferred term
- preferred term

13.1.8 Presentation of Adverse Events Leading to Withdrawal

All the adverse events leading to withdrawal will be listed for the APRS.

TEAEs leading to withdrawal will be summarized by:

- SOC and preferred term
- preferred term

13.1.9 Presentation of Adverse Events Leading to IMP Infusion Interruption

All the adverse events leading to IMP infusion interruption will be listed for the APRS.

TEAEs leading to IMP infusion interruption will be summarized based on APTS by:

- SOC and preferred term
- preferred term

13.1.10 CCI

[REDACTED]

[REDACTED]

[REDACTED]

[REDACTED]

[REDACTED]

13.2 General Methodology for Other Safety Data

Unless otherwise specified, tables, graphs, and listings will be based on the APTS.

All the tables will be presented by treatment group.

The denominators for the summaries of a given variable will be based on the number of participants with non-missing values at a given visit or during the assessment period.

Descriptive statistics for the safety variables, both absolute values and changes from baseline, will be presented by visit.

The number and percentage of participants with at least one PCS value at any post-baseline assessment time point will be summarized by variable. All available assessments will be included in the evaluation of PCS values.

The number and percentage of participants with values out-of-reference range and/or PCS range will be summarized by variable, visit, and last post-baseline assessment.

For participants with post-baseline PCS values, listings will be provided including all the values for those participants for the variable, with flagging of PCS values and out-of-reference-range values.

All the adverse events occurring in participants with post-baseline PCS values will be listed by treatment group and participant screening number; the listing will include the PCS value, the assessment date, the change from baseline in PCS value, the preferred term for the adverse event, and the start date and stop date of the adverse event. The PCS values and adverse events will be listed in chronological order according to assessment date and the start date of the adverse event.

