18. The patient has a history of clinically significant cardiovascular disease, including uncontrolled hypertension, vascular ischaemia, or thromboembolic events (for example, cerebrovascular accident, deep vein thrombosis, or pulmonary embolism).
19. The patient has had surgery or trauma with significant blood loss <3 months prior to the dose of IMP.
20. The patient has donated blood <3 months prior to the dose of IMP.
21. The patient takes or has taken recent or concomitant medication that is disallowed or has not met the restrictions for a medication that is allowed with restrictions (specified in [Appendix II](#)) or it is anticipated that the patient will require treatment with at least one of these medications during the study.
22. The patient has one or more clinically significant out-of-range vital signs at the Screening Visit.
23. The patient has orthostatic hypotension, defined as a decrease in systolic blood pressure ≥ 20 mmHg from supine to standing, at the Screening Visit or at the Baseline Visit.
24. The patient has a body mass index (BMI) >30 kg/m² at the Screening Visit.
25. The patient has previously tested positive for human immunodeficiency virus (HIV).
26. The patient has tested positive for hepatitis C virus antibody (anti-HCV) or has been tested for hepatitis B serology and is confirmed to have acute or chronic infection (refer to [Appendix III](#) for interpretation).
27. The patient has one or more clinical laboratory test values outside the reference range, based on the blood and urine samples taken at the Screening Visit, that are of potential risk to the patient's safety, or the patient has, at the Screening Visit:
 - a serum creatinine value >1.5 times the upper limit of the reference range
 - a serum total bilirubin value >1.5 times the upper limit of the reference range
 - a serum alanine aminotransferase or aspartate aminotransferase value >2 times the upper limit of the reference range
28. The patient has, at the Screening Visit, an abnormal electrocardiogram (ECG) that is, in the investigator's opinion, clinically significant.
29. The patient has a heart rate-corrected QT interval (QTc) >450 ms (Fridericia's correction) at the Screening Visit, as calculated by the central reading vendor and evaluated by the investigator. The ECG may be repeated if any of the values are out of range or abnormal.

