13.3.3 Potential Drug-induced Liver Injury (DILI)

Signals of DILI will be assessed according to the FDA guideline⁴ using the following criteria:

- ALT or AST $>2\times$, $>3\times$, $>5\times$, $>10\times$, or $>20\times$ ULN
- total bilirubin (BILI) $>2\times$ ULN
- alkaline phosphatase (ALP) $>1.5\times$ ULN
- ALT or AST $>3\times$ ULN AND total bilirubin $>1.5\times$ or $>2\times$ ULN

Participants fulfilling any of the criteria will be listed, and the listing will include all the ALT, AST, BILI, and ALP values for those participants, sorted by assessment date and time in ascending order. If a criterion for a test is fulfilled, the value will be flagged with the highest criterion fulfilled (for example, AST $>3\times$ ULN, $>5\times$ ULN, $>10\times$ ULN, or $>20\times$ ULN).

In addition, assessment time points for participants for whom Hy's Law is potentially fulfilled will also be flagged in the listings (pHYL):

- ALT or AST $>3\times$ ULN AND
- alkaline phosphatase $<2\times$ ULN AND
- total bilirubin $\geq 2\times$ ULN

The number of participants who met any of the criteria specified above at any post-baseline visit will be summarized. In the summaries, each participant will be counted only once using the maximum assessment, or the most severe for the combined criteria. The summaries will

also include the number of potential Hy's Law cases. If any participants fulfil Hy's Law (all 3 criteria fulfilled), information collected related to this finding will be presented in data listings.

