Appendix V

CCI

Table 4 PCS Criteria for ECG Parameters

ECG Parameter	CDISC Term	Unit	PCS Low	PCS High
Absolute Time Interval				
PR interval	PRAG	Msec		≥ 260
QRS interval	QRSAG	Msec		≥ 150
QT interval	QTAG	Msec		≥ 500
Derived Time Interval				
Heart rate	EGHRMN	beats/min	< 50 and decrease ≥ 15	≥ 120 and increase ≥ 15
QTcB interval	QTCBAG	Msec	< 300	> 500 or increase > 60
QTcF interval	QTCFAG	Msec	< 300	> 500 or increase > 60

Increase/decrease is relative to the baseline value.

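### The safety counts in SAP 13.2 and 13.3.3 mix new and pre-existing abnormalities for criteria that take no account of baseline (clearly PR, QRS and ALP), so no rate of new findings by arm is available.

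*SAP*

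**What the plan says.** SAP 13.2 sets the general rule for safety data other than adverse events: "The number and percentage of participants with at least one PCS value at any post-baseline assessment time point will be summarized by variable". It adds "All available assessments will be included in the evaluation of PCS values" and "All the tables will be presented by treatment group". On denominators it says "The denominators for the summaries of a given variable will be based on the number of participants with non-missing values at a given visit", with the whole period of assessment as the alternative; participants abnormal at baseline are not removed.

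SAP 13.3.3 applies the same logic to the liver criteria: "The number of participants who met any of the criteria specified above at any post-baseline visit will be summarized". One of those criteria is ALP above 1.5 times the upper limit of normal (ULN), standing alone.

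The ECG criteria are legible in SAP Appendix V, Table 4. PR (260 ms or more), QRS (150 ms or more) and QT (500 ms or more) are absolute limits. Heart rate needs both a limit and a change of at least 15 beats/min. The upper QTc criterion is met either by a value above 500 ms or by an increase above 60 ms. The table note reads "Increase/decrease is relative to the baseline value".

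Other planned outputs bear on the point. Section 13.2 also provides counts of out-of-range and PCS values by visit, change from baseline by visit, and listings of all values of a variable for participants with a post-baseline PCS value on it. For the liver tests, "the listing will include all the ALT, AST, BILI, and ALP values for those participants". No legible text plans a shift table or a count restricted to participants who did not meet the criterion at baseline.

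**The concern.** Potentially clinically significant values are a named safety endpoint in both documents. The drug is given once, at baseline. A value that met a criterion before the infusion and simply stayed there says nothing about the drug, yet it enters the count for its arm on the same footing as a new finding.

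Elsewhere the SAP draws this distinction. Under 13.1.3 an adverse event that began before treatment counts as treatment-emergent only if it worsens or becomes serious. Under 13.3.2 antibodies present at baseline are summarized apart from those that develop during the trial. The heart-rate criterion builds in a change from baseline. The PCS and liver counts have no such step.

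The arms are small (92, 46 and 92 planned), so one or two carried-over cases can change how a row reads. They can look like a difference between arms when there is none, and they dilute a difference that is real.

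**Working it through.** The documents give no figure for this point, so there is none to reproduce. The check has two parts: which criteria are affected, and how much carried-over cases could matter.

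**1. Which criteria can carry over a pre-existing case**

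Two conditions are needed: the criterion must ignore baseline, and the selection criteria in Protocol 5.3 must let such a participant in.

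| Criterion | Uses baseline? | Screened out? | Affected? |
|---|---|---|---|
| Heart rate | Yes, a change of at least 15 is also required | – | No |
| QTc, increase above 60 ms | Yes | – | No |
| QTcF above 500 ms | No | Exclusion 29 removes QTcF above 450 ms | Little room |
| QT 500 ms or more | No | Largely, through exclusion 29 (below) | Little room |
| ALT or AST, from above 2×ULN | No | Exclusion 27 removes above 2×ULN | Little room |
| Bilirubin above 2×ULN | No | Exclusion 27 removes above 1.5×ULN | Little room |
| ALP above 1.5×ULN | No | No numeric limit | Yes |
| PR 260 ms or more | No | No numeric limit | Yes |
| QRS 150 ms or more | No | No numeric limit | Yes |

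The QT row follows from Fridericia's formula, QTcF = QT / RR^(1/3). With QT = 500 and QTcF no more than 450, RR must be at least (500/450)^3 = 1.372 s. That is a heart rate of 60/1.372 = 43.7 beats/min or lower.

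For PR and QRS the relevant rule is exclusion 28: "The patient has, at the Screening Visit, an abnormal electrocardiogram (ECG) that is" clinically significant in the investigator's opinion. An ECG judged not clinically significant does not exclude the patient.

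Where the table says little room, a case could still arise between screening and dosing. The limits apply at the Screening Visit, while the safety baseline (SAP 4.1) is the last valid value before the infusion, normally 28 to 30 days later.

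**2. How much carried-over cases could matter**

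Inputs: planned arm sizes of 92 (high dose), 46 (low dose) and 92 (placebo), from the Protocol synopsis and section 3.1. The share q of participants with a persistent baseline abnormality on a given variable is not in the documents. It is assumed, over a wide range.

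One case adds 1/46 = 2.2 percentage points in the low-dose arm and 1/92 = 1.1 points in either larger arm.

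With no drug effect, let X (high dose) and Y (placebo) be independent Binomial(92, q) counts of carried-over cases. P(X ≥ Y + 2) is the sum of P(X = i)·P(Y = j) over all i ≥ j + 2:

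| Assumed q | Expected cases per 92 | P(high dose exceeds placebo by 2 or more) |
|---|---|---|
| 0.1% | 0.09 | 0.4% |
| 0.25% | 0.23 | 1.8% |
| 0.5% | 0.46 | 5.3% |
| 1% | 0.92 | 12.0% |
| 2% | 1.84 | 20.6% |
| 3% | 2.76 | 25.3% |

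An excess of two or more in the placebo arm is equally likely, because the two arms have the same planned size and the same q.

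Dilution: the reported rate is q + (1 − q) × new-onset rate. Assume new-onset rates of 5% on drug and 1% on placebo, a true ratio of 5.0.

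- q = 1%: (0.01 + 0.99 × 0.05)/(0.01 + 0.99 × 0.01) = 0.0595/0.0199 = 3.0
- q = 2%: (0.02 + 0.98 × 0.05)/(0.02 + 0.98 × 0.01) = 0.0690/0.0298 = 2.3

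**The case against.** The strongest reply is that the affected set is small. A reader might infer from 13.2 and 13.3.3 that every PCS and liver count ignores baseline. That does not hold: heart rate and the QTc increase use it, and the screening limits leave little room for pre-existing transaminase, bilirubin, QTcF or long-QT cases. For ALP, exclusion 27 also opens with a general clause on out-of-range values that put the patient at risk, and exclusion 17 covers clinically relevant hepatic disorders. Both rest on judgement and set no ALP limit, so they narrow the opening without closing it. Tables 2 and 3, for laboratory tests and for vital signs and weight, are redacted. Nothing can be said about whether those criteria carry change conditions, and that is not a fault of the plan.

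A second reply is that baseline status is already visible. The by-visit PCS counts are presented by arm and, since SAP 22.2.1 treats Visit 2 as the Baseline Visit, plausibly include a baseline row. The listings give individual values. This stands in part. By-visit counts are marginal: they do not show whether the participant who is abnormal at Week 4 was the one abnormal at baseline. Listings answer that one participant at a time and yield no rate by arm.

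Third, the size rests on an assumed prevalence. At 0.1% the chance imbalance is negligible. This stands, and it is why a wide range is shown.

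Finally, restricting the count to participants normal at baseline would hide someone whose ALP rose from 1.6 to 4 times ULN. That is a sound objection to replacing the planned count. It does not count against adding to it.

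**Conclusion.** The point holds in a limited form. As written, the any-post-baseline counts in 13.2 and 13.3.3 do not depend on baseline status. For PR, QRS and ALP, new cases and cases present before the infusion are therefore added together, and no planned table gives a rate of new findings by arm.

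The consequence is noise and dilution. A reader might infer that the counts bias the comparison of arms, or that the SAP presents carried-over values as effects of treatment. The documents support neither reading. Randomization balances such cases in expectation, and the SAP calls the counts post-baseline, keeping the term treatment-emergent for adverse events.

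The size cannot be fixed from the documents. A chance excess of two or more carried-over cases on high dose over placebo would occur in about 0.4% of trials at an assumed prevalence of 0.1%, and in about 25% at 3%. These figures assume the planned arm sizes, persistence of the baseline abnormality after dosing, and equal prevalence in the two arms. The tables concerned are descriptive, and the primary analysis is unaffected.

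**What to change.** Keep the planned any-post-baseline count. In SAP 13.2, and for each criterion in the 13.3.3 summary, add one of the following by arm:

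- a row for participants who did not meet the criterion at baseline and met it at least once afterwards, with participants who did not meet it at baseline and have at least one post-baseline value as the denominator; or
- a shift table from baseline status to worst post-baseline status.

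Because the planned count stays, a participant who worsens from an abnormal baseline remains visible. The rule should be written before unblinding, so that it is not chosen after an imbalance has been seen. It needs a sentence in each section and a filter on baseline values already collected. The only downside is a few more table rows.

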13.3 Clinical Safety Laboratory Test Data

13.3.1 Data Presentation

The PCS criteria for the clinical safety laboratory tests are in [Table 2](#).

The clinical safety laboratory test values will be presented in Système International (SI) units.

Fasting lipid and fasting glucose concentrations will be presented in separate tables from the overall laboratory tables.

For urine dipsticks, for which the results are categorical values (for example, negative, trace, 1+, 2+), the number and percentage of participants will be summarized by visit for each test. The microscopy results will be listed by assessment time point for participants with findings.

13.3.2 Anti-drug Antibody Including Neutralizing Antibody Assessments

Analysis of specific anti-Lu AG09222 antibodies is restricted to participants in the APTS who are treated with Lu AG09222.

For participants with pre-existing antibodies at Baseline, the number and percentage of participants who are positive for anti-Lu AG09222 antibody will be summarized. In addition, the number and percentage of participants who develop anti-drug antibodies to Lu AG09222 during the trial will be summarized at each scheduled visit. Denominators for percentages will be the total number of samples taken for the specified visit. For participants with ADA, neutralizing properties of anti-Lu AG09222 antibodies will also be summarized.

Participants with a positive anti-Lu AG09222 antibody result will be listed.

All the adverse events occurring in participants with positive anti- Lu AG09222 antibody or with pre-existing antibodies at Baseline, will be listed. The listing will include the ADA result, the assessment date, the preferred term for the adverse event, and start date and stop date of the adverse event. The ADA results and adverse events will be listed in chronological order according to assessment date and the start date of the adverse event.

In addition, summaries of TEAEs by SOC and preferred term, summaries for TEAEs included in the SMQ Hypersensitivity Narrow by SOC and preferred term will be provided for participants who are ADA-positive and ADA-negative separately.

Furthermore, the potential impact of ADA on efficacy will be explored by providing summaries of change from baseline in monthly migraine days for participants who are ADA-positive and ADA-negative separately.

13.3.3 Potential Drug-induced Liver Injury (DILI)

Signals of DILI will be assessed according to the FDA guideline⁴ using the following criteria:

- ALT or AST $>2\times$, $>3\times$, $>5\times$, $>10\times$, or $>20\times$ ULN
- total bilirubin (BILI) $>2\times$ ULN
- alkaline phosphatase (ALP) $>1.5\times$ ULN
- ALT or AST $>3\times$ ULN AND total bilirubin $>1.5\times$ or $>2\times$ ULN

Participants fulfilling any of the criteria will be listed, and the listing will include all the ALT, AST, BILI, and ALP values for those participants, sorted by assessment date and time in ascending order. If a criterion for a test is fulfilled, the value will be flagged with the highest criterion fulfilled (for example, AST $>3\times$ ULN, $>5\times$ ULN, $>10\times$ ULN, or $>20\times$ ULN).

In addition, assessment time points for participants for whom Hy's Law is potentially fulfilled will also be flagged in the listings (pHYL):

- ALT or AST $>3\times$ ULN AND
- alkaline phosphatase $<2\times$ ULN AND
- total bilirubin $\geq 2\times$ ULN

The number of participants who met any of the criteria specified above at any post-baseline visit will be summarized. In the summaries, each participant will be counted only once using the maximum assessment, or the most severe for the combined criteria. The summaries will

also include the number of potential Hy's Law cases. If any participants fulfil Hy's Law (all 3 criteria fulfilled), information collected related to this finding will be presented in data listings.

